4.6.2.1 Selected Adverse events

Infusion Related Reactions (IRR)

The number and percentage of patients with at least one IRR will be presented by infusion (patients with multiple events within an infusion will count only once). IRR will be selected based on AE CRF page flag. In addition, the total number of IRRs will be summarized (multiple events will be counted). The total and percentage (based on the total number of patients with at least one IRR) will be summarized by most extreme intensity.

IRR will be summarized by intensity and by infusion. For multiple events within a patient, the most extreme intensity will be taken.

IRR will also be summarized by intensity, by infusion and by previous DMT

Infections

A summary table by SOC and PT and listing of all TEAEs and Serious TEAEs infections occurring during the study will be provided. Infections will be selected based the MedDRA SOC of “Infections and Infestations”.

Pregnancies

All pregnancies occurring during the study will be listed.

4.6.3 Delayed return of B cells

Listings of patients whose B-cells have not been repleted after 96 weeks of Follow-up (Prolonged B-cell monitoring) will be provided and added to the CSR report as an appendix, once the data available.

4.6.4 Laboratory Data

Laboratory assessments are performed in local laboratory:

- Hematology (hemoglobin, hematocrit, platelet count, red blood cell [RBC] count, white blood cell [WBC] count, percent and absolute differential count [neutrophils, bands, eosinophils, lymphocytes, monocytes, basophils, other cells]).
- Serum chemistries (AST, ALT, gamma-glutamyl transpeptidase [GGT], total bilirubin, creatinine, random glucose, potassium, sodium)
- Urine dipstick at site (glucose, protein, ketones, blood)
- Viral serology and detection:
 - Hepatitis B (HBsAg and HBcAb confirmed, if positive, by positive viral DNA PCR)
 - For enrolled patients with negative HBsAg and positive total HBcAb, Hepatitis B virus (HBV) DNA (by PCR) must be repeated every 24 weeks
 - Hepatitis C virus (HCV) antibody
- Lymphocytes subtypes: whole-blood samples will be collected to determine the duration of B-cell depletion and recovery (CD19⁺) and T-cell counts (CD4⁺, CD8⁺)

4.6.4.1 General laboratory evaluation

All laboratory assessments (hematology, biochemistry and urine analysis) will be summarized or listed when applicable.

Absolute value and change from baseline values at each visit will be summarized using standard unit. The baseline value will be the last value prior to the first dose of study medication. When laboratory data are presented over time, these laboratory values will be time-windowed into a common visit structure. If multiple values of the same laboratory parameter occur within the same time window, the worst value for that parameter will be presented in the summary table.

A summary of the number and percentage of patients with normal/abnormal laboratory outcomes based on normal laboratory ranges will be produced for each parameter and visit.

In addition, for the liver laboratory parameters, the number and percentage of patients with an elevated post-baseline AST or ALT level during the 96-week treatment period will be summarized and a Hy's law analysis will be performed.

4.6.4.2 Lymphocytes evaluation

All lymphocytes parameters (CD4, CD8 and CD19) will be summarized using absolute count and change from baseline values at each visit.

In addition, the median CD19 cell count will be displayed graphically over time from the first infusion of study medication. At each time point, a summary of the number and percentage of patients whose CD19 counts have repleted will be produced. Repletion is defined as the CD19 count having returned to their baseline value or lower limit of normal, whichever is lowest.

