**Figure 4 Follow-up: Variable B-Cell Monitoring Period**

During the Follow-up Period, patients will be formally assessed at clinical visits every 24 weeks and by telephone contacts every 8 weeks. If further B-cell monitoring is required and the patient is not receiving any other B-cell targeted therapy, assessments will take place at clinical visits every 24 weeks and by telephone contacts every 8 weeks until the B-cells are repleted. See [Appendix 2](#) for further details.

After initiation of study drug, all adverse events will be reported until 96 weeks after the end of the Treatment Period but may be extended in patients whose B-cells take longer to replete.

Related SAEs must be collected and reported regardless of the time elapsed from the last study drug administration, even if the study has been closed.

For patients withdrawing from treatment early, every effort should be made to complete the Follow-up Period and all related assessments regardless of whether or not they receive alternative treatment for MS.

A dedicated (scheduled or unscheduled) follow-up clinic visit directly prior to the start of an alternative MS treatment is required in order to assess the patient's clinical status and safety parameters (assessments to be performed as per [Appendix 2](#), Schedule of Assessments: Follow-up including further B-cell monitoring period).

Patients who receive alternative MS therapies that may decrease B-cell levels will only be followed up for 96 weeks; they will not be entered into the prolonged B-cell Monitoring period thereafter.

A structured telephone interview will be conducted by site personnel every 8 weeks between the study visits during the treatment period and follow-up to identify and collect information on any changes in the patient's health status that warrant an unscheduled

visit (including new or worsening neurological symptoms) and possible events or infections.

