#### **4.5.8 Laboratory, Biomarker, and Other Biological Samples**

Laboratory samples can be taken up to 2 weeks prior to the scheduled study visit. Results should be available prior to dosing, except for anti-JCV antibodies (plasma samples

collected and stored centrally), which will be analyzed upon request, and CD8 and CD19 (no interference with re-treatment).

Pre-infusion laboratory samples should be drawn so that routine laboratory test results are available for review before the infusion, unless otherwise specified.

Routine laboratory assessments (performed in local laboratory) will include the following:

- Hematology (hemoglobin, hematocrit, platelet count, red blood cell [RBC] count, white blood cell [WBC] count, percent and absolute differential count [neutrophils, bands, eosinophils, lymphocytes, monocytes, basophils, other cells]).
- Serum chemistries (AST, ALT, gamma-glutamyl transpeptidase [GGT], total bilirubin, creatinine, random glucose, potassium, sodium)
- Urine dipstick at site
- Pregnancy test: All women of childbearing potential (including those who have had a tubal ligation) will have a serum pregnancy test at screening. A urine pregnancy test should be performed prior to methylprednisolone infusion in subsequent doses. If a urine pregnancy test is positive, it must be confirmed by a serum pregnancy test. The follicle-stimulating hormone (FSH) test is only applicable to confirm postmenopausal status in female patients.
- Viral serology and detection:
  - Hepatitis B (HBsAg and HBcAb confirmed, if positive, by positive viral DNA PCR)
  - For enrolled patients with negative HBsAg and positive total HBcAb, Hepatitis B virus (HBV) DNA (by PCR) must be repeated every 24 weeks
  - Hepatitis C virus (HCV) antibody
- Lymphocytes subtypes
  - Whole-blood samples will be collected to determine the duration of B-cell depletion and recovery (CD19+) and T-cell counts (CD4+, CD8+)

Additional laboratory samples will be collected:

- Plasma samples for anti-JCV antibody assessments at baseline, 1 year and end of study. Samples will be stored in a central laboratory until one year after last patient last visit (LPLV) for further analysis upon request.

For sampling procedures, storage conditions, and shipment instructions, see the laboratory manual.

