### **Delayed return of peripheral B cells**

Treatment with ocrelizumab leads to rapid depletion of CD19+ B cells in blood by 14 days post treatment (first time-point of assessment) as an expected pharmacologic effect. This was sustained throughout the treatment period. The longest follow up time after the last ocrelizumab infusion from Phase II Study WA21493 in 51 patients, indicates that the median time to repletion (returned to baseline/LLN whichever occurred first of B cells was 72 weeks (range 27 – 175 weeks). Patients with prolonged B-cell depletion should be monitored until their B-cells have repleted.

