4.6 SAFETY ANALYSES

The safety outcome measures comprise the following: the incidence and nature of all adverse events, including findings on vital sign measurements, physical and neurological

examinations, clinical laboratory tests, locally reviewed MRI for safety (non-MS CNS pathology), and concomitant medications.

The safety analysis will be performed on the ITT population.

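### The percentage of patients with CD19 repletion has no stated time origin, nothing is timed from the last infusion, and no rule covers CD19 values after another B-cell-lowering therapy

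*SAP*

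**What the plan says.** Protocol 5.1.1.1 lists delayed return of peripheral B cells among the identified risks. Its reference figure is a median time to repletion of 72 weeks (range 27 to 175). It is timed from the last dose: "The longest follow up time after the last ocrelizumab infusion from Phase II Study WA21493 in 51 patients". Protocol 4.5.8 gives the reason for sampling: "Whole-blood samples will be collected to determine the duration of B-cell depletion and recovery".

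The SAP plans these outputs:

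- **Plot (4.6.4.2):** "the median CD19 cell count will be displayed graphically over time from the first infusion of study medication".
- **Percentage repleted (4.6.4.2):** "At each time point, a summary of the number and percentage of patients whose CD19 counts have repleted will be produced". No time origin is given. The definition is: "Repletion is defined as the CD19 count having returned to their baseline value or lower limit of normal, whichever is lowest".
- **Counts and changes by visit (4.6.4.2),** on the general safety set: "The safety analysis will be performed on the ITT population". For laboratory data shown over time, 4.6.4.1 adds that "these laboratory values will be time-windowed into a common visit structure", without naming the anchor.
- **Listing (4.6.3)** of patients not repleted after 96 weeks of follow-up.

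On other therapies, Protocol 3.1.4 says: "Patients who receive alternative MS therapies that may decrease B-cell levels will only be followed up for 96 weeks". They are excluded only from the prolonged monitoring that follows. Lymphocyte subtypes are sampled at the 24-weekly follow-up visits (Protocol Appendix 2). The SAP does not say how CD19 values after the start of such a therapy are handled.

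**The concern.** The useful question about this risk is how long depletion lasts after the last dose. A percentage by calendar position in the study answers that only if everyone at that position is equally far from the last dose. Early stoppers are not. A CD19 count held down by a later drug also says nothing about recovery from ocrelizumab, yet without a rule it would by default enter the table as not repleted. At stake is whether the study can give a figure comparable with the 72-week reference, which is the stated purpose of the samples.

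**Working it through.** The plan gives no CD19 calculation to reproduce, so the check starts from the visit schedule.

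**1. Weeks since last infusion, by study week.** Formula: study week minus week of last infusion. The last infusion falls at Week 2, 24, 48 or 72 after one, two, three or four doses (Protocol Table 1).

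| Study week | 1 dose | 2 doses | 3 doses | 4 doses (completer) |
|---|---|---|---|---|
| 96 | 94 | 72 | 48 | 24 |
| 120 | 118 | 96 | 72 | 48 |
| 144 | 142 | 120 | 96 | 72 |
| 192 | 190 | 168 | 144 | 120 |

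For completers alone the axis is shifted by a constant 72 weeks. The mixing comes from early stoppers.

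**2. Weeks since last infusion, by follow-up visit.** Visit 1 for a completer is 96 + 24 − 72 = 48 weeks after the last infusion. For an early stopper, Protocol Appendix 2 counts 24 weeks from the early discontinuation visit, so the interval is 24 weeks plus a patient-specific gap. SAP Appendix 3 counts from the last infusion, so it is 24 weeks. The two appendices disagree. Under the SAP anchor completers and early stoppers always differ at the same visit. Under the protocol anchor they differ unless the gap is also 24 weeks.

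**3. Selection at late times.** After 96 weeks of follow-up only non-repleted patients continue. A one-dose patient whose discontinuation visit fell before Week 24 has finished those 96 weeks before Week 24 + 96 = 120. If repleted, that patient is no longer sampled. Late percentages are therefore also selected towards non-repletion.

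**4. Assumed recovery curve.** The documents give no distribution. Assumption: log-normal with median 72 weeks, scaled so that the expected extremes of 51 patients match the reported range. The extreme normal score is Φ⁻¹((51 − 0.375)/(51 + 0.25)) = 2.251. The log-SD is ln(72/27)/2.251 = 0.436 from the minimum and ln(175/72)/2.251 = 0.395 from the maximum. The proportion repleted at t weeks is Φ(ln(t/72)/log-SD):

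| Weeks since last infusion | 24 | 48 | 72 | 96 | 120 |
|---|---|---|---|---|---|
| Repleted | 0.3-0.6% | 15-18% | 50% | 74-77% | 88-90% |

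**5. Effect of pooling.** The share f of early stoppers among sampled patients is assumed. They are split equally over last dose 1, 2 and 3 and taken as all still sampled. Pooled percentage = f × (stopper average) + (1 − f) × (completers).

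- Week 96: the stopper average is about 47%. For f = 10%, 0.1 × 46.7 + 0.9 × 0.3 = 4.9%. For f = 10%, 20% and 30% the results are about 5%, 10% and 14%, against under 1% for completers alone.
- Week 120: the stopper average is 71-72%. For f = 20%, 0.2 × 72.1 + 0.8 × 15.2 = 27% (28% with the larger log-SD). For f = 50% it is 44%. Completers alone: 15-18%.
- Week 144: 54%, 57% and 61% for f = 10%, 20% and 30%, against 50%.
- Week 192: 89-93% over the same shares, against 88-90%.
- Follow-up visit 1, SAP anchor, f = 20%: 0.2 × 0.3 + 0.8 × 15.2 = 12%, or 0.2 × 0.6 + 0.8 × 17.6 = 14%, against 15-18%. Here the error has the opposite sign.

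Figures after Week 96 ignore the selection in step 3.

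**6. Effect of another therapy.** Assumption: a share q of followed patients starts it before repletion and then cannot replete. At 120 weeks after the last infusion the percentage is multiplied by (1 − q). It falls from 88-90% to 84-86% (q = 5%), 79-81% (q = 10%) or 70-72% (q = 20%).

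**The case against.** Much of the other side stands.

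- **The time origin.** A reader might infer that repletion itself is timed from the first infusion. The text does not say so: those words govern the median plot, and the origin of the percentage is simply missing.
- **Patients still on treatment.** A reader might also infer that one study week mixes patients still being dosed with completers. Dosing follows fixed study weeks, so apart from visit windows, delays and pregnancy interruptions, continuing patients stand at the same point. The first infusion is a natural origin for on-treatment visits.
- **Other therapies.** No sentence says that values after a switch count as non-repletion. That follows only from the absence of a rule and the use of the ITT set. Protocol 4.4.2 says lymphocyte-depleting agents should not be given while the patient is B-cell depleted, and switchers to marketed ocrelizumab do not enter follow-up. Both limit the scenario. They do not remove it, because Protocol 3.1.4 and Appendix 2 expressly provide for patients on such therapies.
- **Other outputs.** The percentage is not the only output: the 4.6.3 listing is anchored to follow-up. A listing, however, gives no estimate of duration.
- **Size.** If every early stopper had one dose only, Week 120 would read 31% to 52% with 20% to 50% stoppers (log-SD 0.415). That is an extreme split, and many of those patients could have left follow-up by then.
- **Method.** With 24-weekly sampling, ordinary Kaplan-Meier dates repletion late. SAP 4.4.2.8 and 4.4.2.9 dropped lesion-onset analyses for the same reason. This argues for an interval-censored estimate, not for omitting the analysis.

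Finally, the study is exploratory and this output is descriptive. With fewer than 50 patients with data, SAP 2.4 plans a listing only.

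**Conclusion.** The point holds in a limited form. The percentage repleted has no stated origin, and under either available reading it pools patients at different times since their last dose. No output can be set directly against the 72-week reference, and CD19 values after another B-cell-lowering therapy have no rule. It would go too far to say that the planned output does not measure recovery at all: for completers it is a known shift, and under the assumed curve the pooling error shrinks to a few points by Week 192.

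The size is not known. It rests on the assumed log-normal curve and on the shares of early stoppers and therapy starters, none of which the documents give. The share of early stoppers among those sampled after Week 96 may exceed their share of enrolment, because completers who enter the extension study or switch to marketed ocrelizumab do not enter follow-up. No primary or secondary efficacy result is affected. The change is worth making because a better analysis is available from data already collected.

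**What to change.** In SAP 4.6.4.2:

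- Keep the first-infusion plot for on-treatment visits.
- For patients who have stopped ocrelizumab, add time from last infusion to CD19 repletion with the existing definition. Use Kaplan-Meier or, given the sampling interval, an interval-censored estimate, with estimates at 24-week steps.
- Censor at the last CD19 sample before any other B-cell-lowering therapy, and otherwise at the last CD19 sample. Report how many are censored for the first reason.

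In the 4.6.3 listing, and wherever fewer than 50 patients leave only listings, show weeks since last infusion and flag later B-cell-lowering therapy. Reconcile the follow-up visit anchors in Protocol Appendix 2 and SAP Appendix 3.

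The cost is SAP text and one additional output. CD19 results, infusion records and follow-up medication are already collected, SAP 4.2 already counts later DMT use, and Protocol 3.1.4 requires a visit directly before an alternative MS treatment starts. The drawbacks are fewer patients at risk at later times and censoring at a therapy switch that may be informative, which is why the number so censored should be shown.

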4.6.5 Vital Signs

Vital signs will include measurements of heart rate, systolic and diastolic blood pressures, and temperature.

Each parameter of vital sign will be summarized using descriptive statistics at all timepoints.

4.6.6 Physical and neurological examinations

Physical examinations will include an evaluation of head, eye, ear, nose, and throat (HEENT), cardiovascular, dermatological, musculoskeletal, respiratory, and gastrointestinal systems.

Neurological examinations will be used to distinguish relapse in MS from another neurological (non-MS) disorder.

In case of abnormality, number and percentage of patients in each category ("MS relapse", "Disease progression" and "other").

4.6.7 Locally reviewed MRI

Non-MS pathology that is reported by the local safety radiologist will be listed.

4.6.8 Concomitant medications

Concomitant medications (defined as treatment started after baseline visit) will be summarized by frequency tables according to the Anatomic Therapeutic Chemical (ATC) classification system using the WHO Drug dictionary.

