### **4.3.3 Prophylactic Treatment**

Premedicate with 100 mg of methylprednisolone (or an equivalent), administered by slow IV infusion, to be completed approximately 30 minutes prior to each ocrelizumab infusion and an antihistaminic drug (e.g., diphenhydramine) approximately 30 – 60 minutes before each ocrelizumab infusion to reduce the frequency and severity of IRRs. The addition of an antipyretic (e.g., acetaminophen/paracetamol) may also be considered.

Any overdose or incorrect administration of methylprednisolone should be noted on the Pre-Infusion Prophylactic Treatment eCRF. Adverse events associated with an overdose or incorrect administration of methylprednisolone and antihistaminic drug should be recorded on the Adverse Event eCRF.

Patients administered a sedating antihistamine for the treatment or prevention of IRRs should be given appropriate warnings concerning drowsiness and potential impairment of ability to drive or operate machinery.

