### **4.4 CONCOMITANT THERAPY**

Concomitant therapy includes any medication (e.g., prescription drugs, over-the-counter drugs, vaccines, herbal or homeopathic remedies, nutritional supplements) used by a patient within 6 weeks prior to the screening visit to the study completion/ discontinuation visit. All such medications should be reported to the investigator and recorded on the Concomitant Medications eCRF.

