#### **4.4.1 Permitted Therapy**

Patients who use oral contraceptives, hormone-replacement therapy, or other maintenance therapy should continue their use.

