2.2.5 Safety Outcome Measures

The safety and tolerability endpoints are:

- Rate and severity of adverse events
- Changes in vital signs, physical and neurological examinations, clinical laboratory results, locally reviewed MRI for safety (non-MS CNS pathology) and concomitant medications (including pre-medications and medications used during and following ocrelizumab administration).

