4. STATISTICAL METHODS

For continuous variables, descriptive statistics (e.g., number of patients [n], mean, standard deviation [SD], median, 25th and 75th percentiles, minimum, maximum) will be calculated and summarized.

For categorical variables, the number and percentage in each category will be displayed.

Statistical methods for analysis of efficacy variables are detailed in the Efficacy Analyses section below.

Unless otherwise specified, statistical tests will be two-sided and the statistical significance level will be 5%. Corresponding 95% CIs will be presented as appropriate. Although multiple statistical tests may be conducted, no adjustments to the Type 1 error rate will be made.

The analyses outlined in this SAP supersede those specified in the protocol.

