Appendix 2: Schedule of Assessments: Screening through the End of Treatment Period

Visit	Screening	Treatment Period							Early study treatment discontinuation evaluation ^q	Follow-Up ^a Refer to Appendix 3
	1	2 (Baseline)	3	4	5	6	7	8		
Week	-4 to -1 weeks	1	2 (±2 days)	8 (±3 days)	24 (±14 days)	48 (±14 days)	72 (±14 days)	96 (±14 days)		
Informed consent ^b	X									
Medical history and demographic data ^c	X									
Review inclusion & exclusion criteria	X	X								
Physical examination ^d	X	X	X		X	X	X	X	X	
Height and weight	X									
Vital signs ^e	X	X	X		X	X	X	X	X	
Laboratory Assessments										
Hematology, chemistry, urinalysis ^f	X	X	X		X	X	X	X	X	
Pregnancy test ^g	X	X	X		X	X	X	X		
Hepatitis screening ^h	X									
Hepatitis B virus DNA test ^h	X									
Lymphocytes subtypes sample ⁱ		X	X		X	X	X	X	X	
Plasma anti-JCV antibodies sample ^j		X				X		X	X	
EDSS score ^k	X	X			X	X	X	X	X	
Brain MRI ^r	X ^s			X	X	X		X	X	
Neurological examination ^l	X	X	X		X	X	X	X	X	
Recording of potential relapses		X	X		X	X	X	X	X	
Adverse event assessment ^m		X	X		X	X	X	X	X	
Patient Reported Outcomes		X			X	X		X	X	
BICAMS assessment ^t		X				X		X		

Visit	Screening	Treatment Period							Early study treatment discontinuation evaluation ^q	Follow-Up ^a Refer to Appendix 3
	1	2 (Baseline)	3	4	5	6	7	8		
Week	-4 to -1 weeks	1	2 (±2 days)	8 (±3 days)	24 (±14 days)	48 (±14 days)	72 (±14 days)	96 (±14 days)		
Concomitant treatment review		X	X		X	X	X	X		
Methylprednisolone and antihistaminic drug premedication ⁿ		X	X		X	X	X			
Ocrelizumab administration ^o		X	X		X	X	X			
Telephone contact every 8 weeks ^p				X					(X)	

ALT = alanine aminotransferase; ANC = absolute neutrophil count; AST = aspartate aminotransferase; BICAMS= Brief International Cognitive Assessment for Multiple Sclerosis; eCRF = electronic Case Report Form; EDSS = Expanded Disability Status Scale; FSH = follicle-stimulating hormone; GGT = gamma-glutamyl transpeptidase; HBcAb = hepatitis B core antibody; HBsAg = hepatitis B surface antigen; HBV = hepatitis B virus; hCG = human chorionic gonadotropin; HepCAb = hepatitis C; IV = intravenous; JCV = John Cunningham virus; MRI = magnetic resonance imaging; MS = multiple sclerosis; PCR = polymerase chain reaction; PML = progressive multifocal leukoencephalopathy; RBC = red blood cell; WBC = white blood cell.

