- ^l Neurological examinations will be used to distinguish relapse in MS from another neurological (non-MS) disorder. Potential relapses should be recorded throughout the treatment period. Investigators will also screen patients for signs and symptoms of PML by evaluating neurological deficits localized to the cerebral cortex, such as cortical symptoms/signs, behavioral and neuropsychological alteration, retrochiasmal visual defects, hemiparesis, cerebellar symptoms/signs (e.g., gait abnormalities, limb incoordination). Patients with suspected PML should be withheld from ocrelizumab treatment until PML is ruled out by complete clinical evaluation and appropriate diagnostic testing. A patient with confirmed PML should be withdrawn from the study.
- ^m All adverse events should be reported until 96 weeks after the last dose of study drug. After this period, the investigator should report any serious and non-serious adverse events that are believed to be related to prior study drug treatment (see Sections [5.3.1](#) and [5.6](#)).
- ⁿ All patients must receive prophylactic treatment with 100 mg methylprednisolone, administered by slow IV infusion, to be completed approximately 30 minutes before the start of each ocrelizumab infusion, and an antihistaminic drug (e.g., diphenhydramine) approximately 30 – 60 minutes before each infusion of ocrelizumab.
- ^o Ocrelizumab will be administered as two 300-mg IV infusions in 250 mL 0.9% sodium chloride each on Days 1 and 15 and one 600-mg infusion in 500 mL 0.9% sodium chloride every subsequent dose (i.e., every 24 weeks) for a maximum of 72 weeks. It is anticipated that the patient will need to stay at the hospital or clinic for a full day for the infusion visits.
- ^p A structured telephone interview will be conducted by site personnel every 8 weeks (± 3 days) to identify and collect information on any changes in the patient's health status that warrant an unscheduled visit (including new or worsening neurological symptoms) and possible events or infections. No telephone contact is needed in weeks where patient is performing on-site visits (week 24, 48, 72 and 96).

- ^q If the subject discontinues treatment early, all efforts should be made to perform the Early study treatment discontinuation evaluation visit as soon as possible after discontinuation from treatment period. Otherwise, reasons for discontinuation will be captured via telephone call.

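### The concomitant-medication tables in SAP 4.6.8 count only drugs started after the baseline visit, so continued medicines and, read literally, drugs given at the first infusion are left out

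*SAP*

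**What the plan says.** SAP 4.6.8 plans frequency tables by ATC class and fixes their content by start date: "Concomitant medications (defined as treatment started after baseline visit".

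SAP 2.2.5 lists the safety endpoints. One bullet opens by speaking of changes in several measures and ends with "concomitant medications (including pre-medications and medications used during and following ocrelizumab administration". Protocol 2.2 has the same wording.

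Protocol 4.4 tells sites to record on the Concomitant Medications eCRF any medication "used by a patient within 6 weeks prior to the screening visit to the study completion/ discontinuation visit". Protocol 4.4.1 adds: "Patients who use oral contraceptives, hormone-replacement therapy, or other maintenance therapy should continue their use". Protocol 4.1.2 admits patients on fampridine only if the dose was stable for at least 30 days before screening, and prefers that it stay stable over the 96 weeks.

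In the schedule (SAP Appendix 2, Protocol Appendix 1) the row "Methylprednisolone and antihistaminic drug premedication" is marked at the baseline visit and at each later infusion visit. A footnote makes it universal: "All patients must receive prophylactic treatment with 100 mg methylprednisolone".

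SAP section 4 settles precedence: "The analyses outlined in this SAP supersede those specified in the protocol".

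**The concern.** Concomitant use normally means use during treatment, whatever the start date. A start-date rule describes something else, namely new prescriptions. Under it, chronic medicines that are on board at every infusion are invisible, because by design they began before the study did.

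This matters most for reading infusion safety. Protocol 4.3.2.1, 4.4.2 and 5.1.1.1 all raise hypotension during infusion and link it to antihypertensive treatment. Long-standing antihypertensive use is the background a reader would look for, and the table would not show it. Protocol 5.1.1.1 also says that infusion-related reactions were reported more often with the first infusion. Drugs given to treat a reaction at that visit are the ones a literal reading drops. A reader who meets the table without its definition could take it for total co-medication.

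**Working it through.** The plan states no figure on this point, so the check is a comparison of texts plus one count.

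**Step 1. Apply the SAP 4.6.8 rule to each kind of medicine.**
- Started before baseline and continued (Protocol 4.4.1 maintenance therapy, stable fampridine): the start date precedes baseline, so it is excluded. There is no ambiguity.
- Given at the baseline visit (first premedication, any drug for a Day 1 reaction): it starts at that visit, not after it. It is excluded if the wording is taken literally and included if the author meant on or after.
- Started at any later time: included.

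**Step 2. Compare with the endpoint.** SAP 2.2.5 names pre-medications and drugs used during and following administration. The first administration takes place at the baseline visit, so a literal start-after-baseline rule cannot cover the first of these occasions.

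**Step 3. Look for another table that fills the gap.**
- SAP 4.3 summarises prior DMTs only.
- SAP 4.6.1 summarises ocrelizumab exposure only.
- SAP 4.6.2.1 summarises infusion-reaction and infection events, not the drugs given for them.

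The SAP text specifies no summary of ongoing non-DMT medicines or of premedication.

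**Step 4. Count the premedication occasions.** The schedule gives Day 1, Day 15, Week 24, Week 48 and Week 72, which is 5. The literal rule drops the Day 1 occasion: 1/5 = 20% of scheduled occasions for a patient who receives every infusion.

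**Step 5. Convert occasions to patients.** A per-patient ATC table counts a patient once per class if any qualifying record exists. If each infusion's premedication is recorded separately, a patient premedicated again on Day 15 or later still counts.
- The patient-level loss is about N × p, where N is the number treated and p is the proportion with no infusion after Day 1.
- N is about 750 as planned. The documents give no value for p.
- Each percentage point of p is 0.01 × 750 = 7.5 patients.

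Drugs used only on Day 1, such as treatment for a first-infusion reaction, are lost whatever p is.

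**Step 6. Size of the loss of continued medicines.** The documents give no counts of baseline medication, so this cannot be computed.

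**The case against.** Four points on the other side have weight.

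- **The endpoint concerns changes.** A table of newly started drugs is a reasonable way to show change, so a reader who infers that SAP 2.2.5 requires total co-medication goes beyond its wording. This stands for continued medicines. It does not explain leaving out first-infusion premedication or drugs used during that infusion, because the endpoint names both kinds.
- **Protocol 4.4 is a recording window.** It tells sites what to enter on the eCRF and is not an analysis definition, so it would be too strong to say that the SAP contradicts a protocol definition. The remedy below departs from that window as well, since it leaves out drugs stopped before Day 1. What remains is that the SAP tabulates less than sites collect.
- **The Day 1 premedication loss is small per patient.** Someone might infer that premedication vanishes for all of about 750 patients. It does not, because it recurs at four later infusions. It also appears to have its own page: Protocol 4.3.3 says errors in giving methylprednisolone "should be noted on the Pre-Infusion Prophylactic Treatment eCRF". The documents do not say whether that page feeds the 4.6.8 tables. A frequency table of a mandatory drug also tells the reader little.
- **Nothing downstream depends on the table.** No planned estimate, interval or test uses it. The definition is printed in the SAP, and the data are still collected. SAP 2.4 also mentions a separate output list that is not available here, so extra tables cannot be ruled out.

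None of this supplies a planned summary of ongoing medicines. The SAP text names none, and the SAP governs the analysis.

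**Conclusion.** The point holds as a minor one. SAP 4.6.8 leaves continued medicines out of the only concomitant-medication summary the SAP specifies. On a literal reading it also leaves out drugs given at the baseline visit. The result is an incomplete description of a listed safety endpoint. No efficacy analysis, sample-size figure or error rate is affected, and no data are lost.

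The exclusion of continued medicines rests on no assumption. The Day 1 exclusion assumes that a programmer implements the start-after-baseline wording as written. The limit on its size assumes a per-patient table with premedication recorded separately at each infusion; the loss then falls mainly on patients with no infusion after Day 1 and on Day 1-only drugs. The proportion of medication records omitted is unknown.

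**What to change.** Replace the definition in SAP 4.6.8 so that concomitant medication is any medication taken on or after the date of the first infusion during the treatment period, regardless of start date. The first-infusion date is also the safer anchor, because SAP 4.4.1 allows that a baseline visit may be dated after first dosing.

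Then add two displays:
- a sub-table of medicines newly started after baseline, which serves the endpoint's interest in change;
- a summary of premedication by infusion, taken from its own eCRF page. Confirm first that this page holds routine premedication, since Protocol 4.3.3 mentions it only for overdose and incorrect administration.

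The cost is one changed SAP sentence and slightly more tabulation. No new data collection is needed, since Protocol 4.4 already has sites record these medicines.
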